9.1.2. Biomarker (NfL) Analysis

Biomarker assessments include:

- Change from Baseline to Weeks 26, 52, 65 and 78 in plasma NfL protein
- Relationship between Baseline NfL and changes from Baseline in select efficacy endpoints
- Relationship between changes from Baseline to Weeks 26, 52, 65 and 78 in NfL and select efficacy endpoints for pridopidine 45 mg bid vs. placebo

- Proportion of participants with stabilization or improvement in change from Baseline to Weeks 26, 52, 65 and 78 in plasma NfL protein

Objectives of the NfL analysis

- (1) To investigate the effect of pridopidine 45 mg bid vs. placebo on changes in log-transformed plasma NfL from Baseline to Weeks 26, 52, 65 and 78 (as pg/mL, with \log_2 transformation), accounting for the effects of Baseline NfL and other possible factors as listed below.

The main analysis is based on change from Baseline in $\log_2(\text{NfL})$ over time, and similar analysis will be repeated for actual values of \log_2 -transformed plasma NfL levels. Analysis will be performed on observed data using MMRM separately for actual values and change from Baseline over time. The model will include the following fixed effects: *treatment*, *categorical weeks*, *Baseline $\log_2(\text{NfL})$* , *Age and BMI at Baseline*, randomization stratification factors (*HD stage and neuroleptic use at Baseline*), interaction effect of *treatment*categorical weeks*. The spatial power covariance matrix for repeated observations within participants will be used. The denominator degrees of freedom for the tests of fixed effects will be approximated by Kenward-Roger method.

Each fixed effect will be tested at a type I error level ≤ 0.05 , two-sided and the 95% two-sided confidence intervals (CI) of the parameters will be computed. The LSMS of actual values and change from Baseline in $\log_2(\text{NfL})$ and associated SE for each treatment group, as well as the LSM, 95% CI, and p-value for the treatment difference (pridopidine 45 mg bid vs. placebo) will be presented at all visits in analysis. The LSM of change from Baseline in $\log_2(\text{NfL})$ at each visit will be back transformed to the percent change in NfL as $2^{\text{LSM}} \times 100 - 100$. The 95% CI of the LSM will also be back transformed.

In addition, actual values, change from Baseline to each visit of $\log_2(\text{NfL})$ and actual value, and % change from Baseline in raw NfL value will be summarized using descriptive statistics and graphics where applicable.

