The LSM and the associated SE of the Baseline NfL-adjusted efficacy endpoint at some specified Baseline NfL values (such as median, first quartile [low level], and third quartile [high level]) for each treatment group, and the LSM, 95% CI and p-value for the treatment difference (pridopidine 45 mg bid vs. placebo) will be presented for all visits.

To investigate the additional covariates that may have an effect on the efficacy endpoints, more covariates will also be added one at a time or altogether to above model: CAG repeats, age, sex, CAP score, BMI, region. When all covariates are added to the model together, a stepwise model selection approach, as described in Objective (1), will be adopted to see the most influential covariates on the change in NfL over time. Each covariate will be tested at a type I error level ≤ 0.05 , two-sided and the 95% two-sided CIs of the parameters will be computed.

(3) To investigate the relationship between change in NfL over time and change in clinical efficacy endpoints including UHDRS-TFC, cUHDRS, Q-Motor [REDACTED], UHDRS-TMS, SDMT and SWR accounting for the effect of pridopidine 45 mg bid vs placebo.

The dependent variables investigated are clinical outcomes such as UHDRS-TFC, cUHDRS, Q-Motor [REDACTED] UHDRS-TMS, SDMT and SWR over time, with one dependent variable fit at a time.

The main analysis is based on change from baseline in both efficacy endpoints and $\log_2(\text{NfL})$, and similar analyses will be repeated for actual values of efficacy endpoints and $\log_2(\text{NfL})$. Analysis will be performed on observed data using MMRM separately for actual values and change from Baseline over time. The model for change from Baseline in a specific efficacy endpoint over time will include the following effects: *treatment*, *categorical weeks*, *Baseline value of efficacy endpoint to be analyzed*, randomization stratification factors (*HD stage* and *neuroleptic use at Baseline*), *change from Baseline in log₂(NfL)*, interaction effects of *treatment*categorical weeks*, *treatment*change from Baseline in log₂(NfL)*. The spatial power covariance matrix for repeated observations within participants will be used. The denominator degrees of freedom for the tests of fixed effects will be approximated by Kenward-Roger method.

The effect of *change from Baseline in log₂(NfL)* by treatment group will be tested at a type I error level ≤ 0.05 , two-sided and the 95% two-sided CI of the parameter will be computed.

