Another simpler approach to perform a simple linear model on the change from Baseline of these clinical outcomes at the specified timepoint may be performed. For Week 65 analysis, the model will include the following effects: *treatment*, Baseline $\log_2(NfL)$, $\log_2(NfL)$ at Weeks 26, 52 and 65, and interaction effects of *treatment** $\log_2(NfL)$ at Baseline and Weeks 26, 52 and 65. Each covariate related to $\log_2(NfL)$ will be tested at a type I error level ≤ 0.05 , two-sided and the 95% two-sided CI of the parameters will be computed.

To investigate the additional possible covariates that can have an effect on change in efficacy endpoints over time, more covariates will also be added one at a time or altogether to the above model: CAG repeats, age, CAP score, BMI, region. When all covariates are added to the model together, a stepwise model selection approach, as described in Objective (1), will be adopted to see the most influential covariates on the change in NfL over time. Each covariate will be tested at a type I error level ≤ 0.05 , two-sided and the 95% two-sided CI of the parameters will be computed.

(4) To investigate the proportion of participants with no increase from Baseline to Weeks 26, 52, 65 and 78 in plasma NfL levels. Other thresholds may also be explored.

The dependent variable is a binary variable which is defined as follows:

$$\text{Dependent variable} = \begin{cases} 1 & \text{if Change from Baseline in } \log_2(NfL) \leq 0 \\ 0 & \text{otherwise} \end{cases}$$

This binary variable dichotomizes changes from Baseline in $\log_2(NfL)$ over time to show whether or not there is a beneficial decrease in $\log_2(NfL)$ from Baseline. Analysis will be performed on the binary data at each visit using logistic regression model. In this model, the log odds of the dependent variable are modelled.

The model will include the following fixed effects: *treatment*, Baseline $\log_2(NfL)$, randomization stratification factors (*HD stage and neuroleptic use at Baseline*), interaction effect of *treatment***Baseline log₂(NfL)*.

Each fixed effect will be tested at a type I error level ≤ 0.05 , two-sided, and the 95% two-sided confidence intervals (CI) of the parameters will be computed. Odds Ratios of treatment effect with their 95% CI at each visit will be presented in analysis.

Subgroup analysis which divides the participants by median Baseline NfL level will be performed for above objectives where applicable.

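### The optional Week 65 NfL linear model omits the endpoint's Baseline value and the randomisation strata, and tests four serial NfL levels one at a time although the objective concerns change in NfL

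*SAP*

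**What the plan says.** Objective (3) in SAP 9.1.2 asks how change in NfL relates to change in TFC, cUHDRS, Q-Motor, TMS, SDMT and SWR. The section's list of assessments words it as "Relationship between changes from Baseline to Weeks 26, 52, 65 and 78 in NfL and select efficacy endpoints".

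The main analysis is an MMRM: "The main analysis is based on change from baseline in both efficacy endpoints and" log2(NfL). Its effects include "Baseline value of efficacy endpoint to be analyzed", HD stage, neuroleptic use, one NfL-change term and that term's interaction with treatment.

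The SAP then adds an option: "Another simpler approach to perform a simple linear model on the change from Baseline of these clinical outcomes at the specified timepoint may be performed". Its effect list is closed. "For Week 65 analysis, the model will include the following effects": treatment, log2(NfL) at Baseline, log2(NfL) "at Weeks 26, 52 and 65, and interaction effects of" treatment with each of those four levels. Each NfL covariate "will be tested at a type I error level" of at most 0.05, two-sided. No joint test is named. The further covariates that may be added under Objective (3) are "CAG repeats, age, CAP score, BMI, region", which do not restore the endpoint's Baseline value or the strata.

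**The concern.** Three features of the optional model differ from the MMRM it simplifies, and the SAP gives no reason for any of them.

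- **Missing adjustment.** Change from Baseline usually depends on the Baseline value. If Baseline status is also related to NfL, the NfL terms absorb that dependence. They can then show a relationship that is not there or hide one that is.
- **Levels instead of change.** The question is about change in NfL, but the model enters four repeated levels and tests each one given the other three. The more stable NfL is within a person, the less each single test can show.
- **Eight separate tests.** Four levels and four interactions are each tested at 0.05.

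At stake is the reading of NfL as a marker of clinical change. Run as written, this model could disagree with the MMRM for reasons unrelated to NfL. No confirmatory conclusion depends on it.

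**Working it through.** **Plan's own figures.** The documents state no power, effect size or between-visit correlation for any NfL model. The only power statements (SAP 3.3) concern the primary endpoint, and they reproduce:

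- 0.7/(1.9×√(2/186)) = 3.553, and Φ(3.553 − 1.960) = 94.4% (stated 94%, N = 372).
- 0.565/(1.9×√(2/240)) = 3.258, and Φ(3.258 − 1.960) = 90.3% (stated 90%, N = 480).

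**Assumptions, none from the documents.** n = 400; common correlation ρ of 0.80-0.95 between NfL visits; NfL signal 2.25% of outcome variance; correlation r of the endpoint's Baseline value with NfL of -0.3 to -0.4; share s of outcome change explained by that Baseline value of 6-9%.

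**1. False relationship from the omitted Baseline value.** With no true NfL effect, the NfL terms falsely explain about x = s×r² of the variance. The noncentrality of the joint 8-df F-test is n×x/(1 − x).

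| s | r | x | Noncentrality | Rejection of a true null |
|---|---|---|---|---|
| 6% | -0.30 | 0.0054 | 2.17 | 13.7% |
| 8% | -0.35 | 0.0098 | 3.96 | 23.1% |
| 9% | -0.40 | 0.0144 | 5.84 | 34.0% |

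Simulation agrees: 14-34% over this range and 22-23% for the middle row, against about 5% once the Baseline value is added. A separate run with n = 372, s = 9%, r = -0.3 and a 4-df test of the NfL main effects gave 24%; the formula gives 24.4%.

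The bias can also hide an effect. In runs with average NfL level as the driver, a 5% signal and the opposite sign of dependence, the unadjusted joint test had 25-73% power, against 94-99% adjusted. Where Baseline status is unrelated to NfL, omission costs only precision: the standard error grows by 1/√(1 − c²), where c is the correlation of the Baseline value with outcome change. That is 0.5%, 5% or 15% for c = 0.1, 0.3 or 0.5.

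**2. Chance findings.** If the eight tests were independent, 1 − 0.95⁸ = 33.7%. Simulated rates of at least one significant result with no relationship run from 26% to 34%. For the four main terms alone, they are 15-16%.

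**3. Power when NfL change is the driver.** Variance inflation for one of four equally correlated levels is (1 + 2ρ)/[(1 − ρ)(1 + 3ρ)]. With signal 0.0225, the slope on change satisfies β² = 0.0225/[2(1 − ρ)]. The noncentrality is:

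- Week 65 term as written: 400×β²/(inflation×0.9775).
- Change term in a model with Baseline NfL plus change: 400×β²×(1 − ρ²)/0.9775.

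Both halve if the reported slope is for one arm rather than averaged over arms.

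| ρ | Inflation | As written, averaged | Change term, averaged | As written, one arm | Change term, one arm |
|---|---|---|---|---|---|
| 0.80 | 3.8 | 68.7% | 81.9% | 40.9% | 52.8% |
| 0.90 | 7.6 | 69.2% | 83.9% | 41.3% | 55.0% |
| 0.95 | 15.1 | 69.4% | 84.8% | 41.5% | 56.1% |

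The loss is 12-15 points by formula. Simulation gives 66-69% against 80-83% averaged and 39-41% against 52-55% in one arm, a loss of about 12-17 points.

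**4. Power when stable level is the driver.** With the same 2.25% signal from average NfL level and ρ = 0.9, averaged over arms, a single level as written has slope β/4 with β² = 0.0225/0.925. Its noncentrality is 400×0.02432/(16×7.57×0.9775) = 0.08, so power is about 6%. In the Baseline-plus-change model the Baseline NfL term has about 85%; simulation gave 82-85%.

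**5. Adjustment alone does not restore single-term power.** At ρ = 0.9, a 5% signal and average or Week 65 level as the driver, the mean single-term rejection rate was 7-16% as written and 6-14% after adding Baseline value and strata. A joint test of the four adjusted levels had 94-99% in every 5% scenario run.

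**The case against.** The strongest reply is that this model hardly matters. It is optional, exploratory, and outside the sequence tested under SAP 5.6, which makes no adjustment for other exploratory efficacy endpoints. The main Objective (3) MMRM has the Baseline value, both strata and a single NfL-change term. Objective (2) tests Baseline NfL with the same adjustments. All of this stands and sets the severity. It does not explain why the simpler model drops the covariates.

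Stronger readings that a reader might infer are not supported:

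- **That the plan would mostly miss a real NfL relationship.** The MMRM addresses it directly, and the documents give no between-visit correlation to show that the four levels nearly duplicate each other. If NfL change explains 5% of outcome variance, the Week 65 term as written has 91-96% power (n = 372, averaged over arms, ρ 0.5-0.95).
- **That power is about 40% against 80-84%.** This sets a one-arm slope against an averaged one. On one footing it is about 40% against 55%, or 68% against 83%.
- **That centring NfL would settle the meaning of the slopes.** Centring leaves the NfL slopes unchanged. Whether a main effect refers to one arm or to the average depends on treatment coding or test type, which the SAP does not fix.
- **That requiring four samples loses 18.5% of participants against 9.75% for two.** These are 1 − 0.95⁴ and 1 − 0.95², which need independent 5% loss at each visit. SAP 5.8.1.2 expects mostly monotone missing efficacy data. If NfL samples follow that pattern, the extra loss is small.

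**Conclusion.** The point holds as a low-severity correction to an optional exploratory model. The omissions and the term-by-term testing are in the text and need no assumption. Their size does: the false-relationship rate of 14-34% needs Baseline status to be related to NfL and to outcome change, and the 12-17 point power loss needs ρ of 0.8-0.95 and a 2.25% signal from NfL change. The power loss is larger if stable level is the driver. The 26-34% chance of at least one significant NfL test needs only that there is no relationship. The defects are distinct: missing covariates cause confounding, while serial levels tested singly cause low power and multiple chances of error. The primary analysis, the hierarchy and the main NfL MMRM are unaffected.

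**What to change.** If the Week 65 linear model is run, revise its effect list in SAP 9.1.2:

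1. Add the Baseline value of the analysed endpoint, HD stage and neuroleptic use, as in the Objective (3) MMRM.
2. Either replace the four NfL levels with Baseline log2(NfL) plus change to Week 65 in log2(NfL), each with its treatment interaction, or keep the levels and prespecify one joint test of the NfL terms.
3. State whether NfL slopes are reported by arm or averaged over arms.

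The cost is a wording change and one program edit; every variable is already collected. The downside is that separate per-visit NfL coefficients are no longer the reported tests.

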9.4.8. Biomarker (NfL) Analysis

Descriptive statistics of plasma NfL levels and log2 transformed NfL levels will be presented by treatment group and visit.

An MMRM will be used to analyze treatment and covariate effects on the change from Baseline in log2 transformed NfL levels.

The impact of log2 transformed Baseline NfL on change from Baseline to post-baseline visits in UHDRS-TFC, cUHDRS, Q-Motor [REDACTED] UHDRS-TMS, SDMT, and SWR accounting for treatment effect and other covariates will also be analyzed using an MMRM.

Furthermore, the change from Baseline to post-baseline visits in above efficacy endpoints in response to change from Baseline in log2 transformed NfL levels will be analyzed using an MMRM model accounting for treatment effects and other covariates.

The proportion of participants with change from Baseline ≤ 0 in log2 NfL levels to post-baseline visits will be presented by treatment group with 95% CI with normal approximation. Other thresholds to dichotomize log2 NfL change will also be explored, and the resulting proportions by treatment group and the difference between treatment groups in the proportions will be presented along with 95% CI.

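### The NfL responder model includes a treatment by Baseline log2(NfL) interaction but names no Baseline NfL value at which the treatment odds ratio and its test apply

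*SAP*

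**What the plan says.** SAP 9.1.2 has four NfL objectives. Objective (4) dichotomises the change from Baseline in log2(NfL) at zero and fits a logistic regression at each visit. The terms are introduced by "The model will include the following fixed effects: *treatment*, Baseline" log2(NfL), followed by HD stage, neuroleptic use and the "interaction effect of *treatment*Baseline log₂(NfL"). On testing it says "Each fixed effect will be tested at a type I error level" of 0.05, two-sided, with 95% confidence intervals of the parameters. On reporting it says "Odds Ratios of treatment effect with their 95% CI at each visit will be presented in analysis". No centring is stated, and no Baseline NfL value is attached to the odds ratio or the test.

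The unit comes from Objective (1), which refers to "changes in log-transformed plasma NfL from Baseline to Weeks 26, 52, 65 and 78 (as pg/mL", with log2 transformation.

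Objective (2) has the same interaction, for continuous efficacy endpoints. It presents adjusted means by arm and the treatment difference "at some specified Baseline NfL values (such as median, first quartile [low level], and third quartile [high level"]). The main model of Objective (1) has no treatment by Baseline NfL term.

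Two other looks at the responder endpoint are planned. Protocol 9.4.8 presents the proportion with change of zero or less by treatment group with a 95% CI. For other thresholds it adds that "the resulting proportions by treatment group and the difference between treatment groups in the proportions will be presented along with 95% CI". SAP 9.1.2 closes with "Subgroup analysis which divides the participants by median Baseline NfL level will be performed for above objectives where applicable".

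**The concern.** Once treatment interacts with a continuous covariate, the model contains a treatment odds ratio for each value of that covariate. A plan that promises treatment odds ratios must say at which value. Objective (4) does not, although Objective (2) does for the same interaction.

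The fixed-effect test is a separate matter. In the model as written, the treatment parameter is the log odds ratio where the covariate equals zero. Since log2(1) = 0 and NfL is in pg/mL, that is a participant with a Baseline NfL of 1 pg/mL. If the trial's Baseline values lie well above that, the test is an extrapolation.

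Two things are at stake. Two competent programmers could report different odds ratios and p-values from the same data, with the choice still open after unblinding. And the literal treatment test could miss a real effect on the proportion with stable or lower NfL, or reject for an effect at a value no participant has.

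**Working it through.** **The plan's own figures.** The documents state no power, responder rate, odds ratio, mean or SD for the NfL responder analysis. The figures they do state are for the primary endpoint, and they reproduce. A difference of 0.7 with SD 1.9 and N = 372 gives 94.4% (stated 94%). A difference of 0.565 with N = 480 gives 90.3% (stated 90%). 372 / (1 − 0.225) = 480. They supply only the sample sizes used below.

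**Step 1: what the treatment parameter is.** Write the log odds as a + b·T + c·x + d·T·x + strata, with x = Baseline log2(NfL) in pg/mL. The treatment log odds ratio at x is b + d·x. The parameter b, whose test and CI are promised, is its value at x = 0, that is at NfL = 2^0 = 1 pg/mL. This is algebra and needs no outside figure.

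**Step 2: its precision.** With 1:1 allocation, approximately,

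SE(b at x = 0) / SE(effect at the mean of x) = sqrt(1 + mean² / SD²).

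Assumed, because the documents give no values: mean log2(NfL) 3 to 5 (8 to 32 pg/mL) and SD 0.7 to 1.0.

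- Mean 3, SD 1.0: sqrt(1 + 9/1) = 3.2
- Mean 5, SD 0.7: sqrt(1 + 25/0.49) = 7.2

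If the SD were as low as 0.4, the ratio at mean 5 would be 12.5.

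**Step 3: power, if the odds ratio is the same at all NfL levels.** An effect with power P at the mean has standardised size 1.960 + z(P) there, that is 2.80 for 80% and 3.24 for 90%. Divide by the SE ratio and compute two-sided power at 0.05.

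| SE ratio | Standardised size (80% / 90%) | Power of literal test (80% / 90%) |
|---|---|---|
| 3.16 | 0.89 / 1.03 | 14.4% / 17.6% |
| 7.21 | 0.39 / 0.45 | 6.7% / 7.3% |

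Over SD 0.7 to 1.0 the range is therefore about 7 to 18%. Extending the SD down to 0.4 lowers the bottom to 5.6%.

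**Step 4: simulation of the Objective (4) model** (800 runs per scenario; mean log2 3.5 to 4.5, SD 0.6 to 1.0; placebo responder rate 40%, assumed).

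| N | True OR | Test at x = 0 | Test with x centred |
|---|---|---|---|
| 372 | 1.8 | 6–9% | 79–81% |
| 480 | 1.8 | 7–12% | 88–90% |
| 372 | 2.0 | 6–14% | 91–92% |
| 480 | 2.0 | 8–13% | 95–98% |

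The model without the interaction has essentially the same power as the centred one. Centring leaves the model fit and the interaction test unchanged. With no effect (OR 1.0), the literal test rejected in 3.4 to 5.8% of runs.

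**Step 5: if the odds ratio varies with Baseline NfL.** Take N = 480, mean 4, SD 0.6 and OR 1.8 at the mean. The OR at 1 pg/mL is 1.8·exp(−4·slope).

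| Slope per log2 unit | OR at 1 pg/mL | Literal test rejects |
|---|---|---|
| −0.5 | 13.3 | 56% |
| +0.5 | 0.24 | 18% |
| +1.0 | 0.03 | 70% |

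In the last two rows every rejection points against pridopidine, although the effect at the mean favours it.

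**The case against.** The strongest reply is that the SAP leaves a gap rather than making an error. It nowhere says the covariate is uncentred, and nowhere equates the reported odds ratio with the exponentiated treatment coefficient. It speaks of odds ratios in the plural. Objective (2) shows that the authors know how to evaluate this interaction, so an unstated convention is quite possible. This stands in part: the odds ratio is undefined, and a reader who infers that the plan fixes it at 1 pg/mL goes beyond the text. It does not dispose of the parameter test, because testing each fixed effect of the model as written means testing at log2(NfL) = 0.

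A reader might also infer that the planned test has almost no power. The documents do not support that as a general statement. They give no NfL mean, SD, responder rate or target odds ratio. The low power also requires a constant odds ratio; when the odds ratio varies, rejection can be frequent, and the difficulty is then what is being rejected.

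Nor does it follow that the trial cannot answer its NfL question. Objective (1) compares the arms on the continuous change in log2(NfL), with a difference, CI and p-value at every visit and no such interaction. The proportions by arm and the median-split analysis are planned as well. They do not fully replace Objective (4), which holds the only adjusted between-arm comparison specified for the responder endpoint. For the zero threshold Protocol 9.4.8 gives proportions by arm, and mentions a between-arm difference only for other thresholds. The median split applies only where applicable and gives no overall effect.

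Finally, NfL is exploratory and outside the testing hierarchy. That stands, and it limits the severity.

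**Conclusion.** The point holds as a specification defect of minor severity. Two statements rest on the text and algebra alone: the treatment odds ratio of Objective (4) is undefined, and the treatment parameter test as written applies at 1 pg/mL.

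The size rests on assumptions. With mean log2(NfL) 3 to 5 and SD 0.7 to 1.0, the standard error is about 3 to 7 times that at the mean. Power of 80 to 90% at the mean becomes roughly 7 to 18% in the literal test if the odds ratio is constant (down to about 6% if the SD is as small as 0.4). If the odds ratio depends on Baseline NfL, the test may reject for an irrelevant or reversed effect. Type I error with no effect is not inflated. No primary, multiplicity-adjusted secondary or safety conclusion depends on this analysis.

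**What to change.** Amend Objective (4) in one of two ways.

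1. Keep the model. Centre Baseline log2(NfL) at its median (or mean), and report the treatment odds ratio, 95% CI and p-value there at each visit, with odds ratios at the first and third quartiles as in Objective (2).
2. Take the overall treatment odds ratio, 95% CI and p-value from the model without the interaction (treatment, Baseline log2(NfL), HD stage, neuroleptic use). Test the interaction in a separate model.

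The first is the smaller change and matches the SAP's own practice. Either costs about one sentence in the SAP; the second adds one model run per visit. Neither needs new data. The choice should be recorded before unblinding, or, if that has passed, declared in the study report as a change to the planned analysis.
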